Probing Cortical Excitability and Cognitive Function With TMS

May 22nd, 2025

NCT03652012

Participants:

[figure not shown]
Forty community-dwelling older adults were enrolled in this study. All participants completed comprehensive neuropsychological assessments to determine cognitive status based on the revised Mayo Clinic criteria for mild cognitive impairment (MCI), which include: (a) a self- or informant-reported cognitive complaint; (b) objective evidence of cognitive impairment; (c) preserved independence in functional abilities; and (d) absence of dementia(Petersen et al., 2014).

Classification of MCI was further supported using the Jak/Bondi actuarial neuropsychological method and the National Alzheimer's Coordinating Center (NACC) Uniform Data Set Version 3.0 Neuropsychological Battery(Weintraub et al., 2018). Participants were classified as cognitively impaired if they scored more than 1 standard deviation below age- and education-adjusted normative data on either: (i) two tasks within the same cognitive domain, or (ii) one task in each of three different domains, consistent with the Jak/Bondi criteria(Jak et al., 2009; Jak et al., 2016).

Based on these criteria, 20 participants were classified as having MCI, while the remaining 20 were demographically matched and served as cognitively normal controls.

Trial Design:

Each participant attended two study visits (Fig. 1). During session 1, participants completed a comprehensive neuropsychological battery. The groups were counterbalanced to include 20 classified as cognitively normal (CN) and 20 classified as MCI.

Session 2 comprised both Magnetic Resonance Imaging (MRI) and Transcranial Magnetic Stimulation (TMS). We acquired functional MRI (fMRI) data both before and immediately upon completion of the TMS protocols. We evaluated resting-state functional connectivity between the stimulation site (M1) and neighboring regions (e.g., somatosensory cortex; S1).

TMS was applied to the primary motor cortex using an infrared-based frameless stereotactic neuronavigation system (Polaris System, Localite Version 3.0.41). Single-pulse protocols were

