The **stimulus-response curve** is evaluated by examining how MEP amplitude—typically measured as peak-to-peak response—varies across different stimulus intensities(Devanne et al., 1997). This relationship follows a sigmoidal trajectory, often called the stimulus-response, recruitment, or input-output curve. The curve is typically modeled using a sigmoidal function, such as Boltzmann’s

equation, by plotting stimulus intensity against corresponding MEP amplitudes. Among the various parameters that can be derived from this function, our analysis focused on the slope of the curve's linear region, which reflects corticospinal excitability (Fig. 2). This outcome measure was collected under two experimental conditions: with a tonic voluntary muscle contraction (20% of max voluntary contraction) or with the corresponding muscle at rest. Half of the participants from each cohort were assigned to each experimental condition.

The **CSP** is the temporary disruption of background voluntary muscle activity immediately following the MEP, resembling electrical silence in the EMG signal (Fig 3). Quantified as the duration of EMG absence following an MEP, CSP is a measure of GABA-mediated intracortical inhibition (Paulus et al., 2008).

Lastly, we assessed the resting-state functional connectivity of the stimulation site (M1). We assessed group differences at baseline as well as group differences in the iTBS-induced change in functional connectivity.

Statistical Design and Analysis

This cross-sectional study examined group differences across the outcome measures described above. Two-sample t-tests compared the MCI and cognitively normal control groups on resting motor threshold (rMT), cortical silent period (CSP), and resting-state functional connectivity. We conducted a two-way factorial ANOVA with Group (MCI vs. control) and Condition (active vs. rest) as between-subject factors for the stimulus-response curve, which included an additional experimental condition. Our primary parameter of interest was the slope of the sigmoidal input-output curve, which reflects corticospinal excitability. We applied a Bonferroni-adjusted significance threshold to account for multiple comparisons across the stimulus-response parameters.

References

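### Single-step Bonferroni across the stimulus-response parameters, slope apparently included, is valid but less efficient than Holm, which keeps the same family-wise bound

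*Combined protocol and SAP*

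**What the plan says.** Under Statistical Design and Analysis, the stimulus-response curve is analysed by a "two-way factorial ANOVA with Group (MCI vs. control) and Condition (active vs. rest) as between-subject factors". One parameter is singled out: "Our primary parameter of interest was the slope of the sigmoidal input-output curve, which reflects corticospinal excitability". The Outcome Measures section has the same emphasis ("our analysis focused on the slope"). The multiplicity rule follows: "We applied a Bonferroni-adjusted significance threshold to account for multiple comparisons across the stimulus-response parameters".

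The document does not name or count the other parameters in that family. It gives no alpha, sidedness, effect size or target power. It does not say whether Group or Group by Condition is the effect of interest, and it documents no testing order. The text is in the past tense throughout, so it describes an analysis already carried out.

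**The concern.** The plan ranks its parameters and then corrects as though they were unranked. If the slope is inside the family, its threshold is alpha/m, where m is the number of parameters, although other procedures with the same guaranteed family-wise error use the allowance better.

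This matters because the sample is small. With 10 participants per cell, a real group difference in slope is easily missed, and a non-significant slope at alpha/m could be misread as showing no difference in corticospinal excitability.

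**Working it through.** The document states no power or sample-size figure, so there is none to reproduce.

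**Inputs from the document**
- Total sample: "Forty community-dwelling older adults were enrolled in this study".
- Groups: "20 participants were classified as having MCI, while the remaining 20 were demographically matched and served as cognitively normal controls".
- Condition: "Half of the participants from each cohort were assigned to each experimental condition". Hence 20/2 = 10 per cell, four cells, and 40 − 4 = 36 error degrees of freedom.

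**Assumptions (not in the document)**
- Family-wise alpha 0.05, two-sided.
- m = 2, 3 or 4 parameters.
- The Group main effect is the effect tested.
- True difference d, in SD units, from 0.3 to 1.2.

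**Step 1: the rules compared.** Bonferroni compares every p-value with 0.05/m. Holm orders the p-values from smallest to largest, compares the j-th with 0.05/(m − j + 1), and stops at the first failure. For m = 3 the thresholds are 0.0167, 0.0167, 0.0167 (Bonferroni) and 0.0167, 0.025, 0.05 (Holm). No Holm threshold is below Bonferroni's, so Holm never rejects less. Its 5% bound needs no added assumption about correlation.

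**Step 2: power for the slope at a fixed threshold.** The standard error of the Group difference is √(2/20) SD, so the noncentrality is d²/(2/20) = 10d². At d = 0.8 this is 6.4. Noncentral F(1, 36) gives:

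| d | at 0.05 | m = 2 (0.025) | m = 3 (0.0167) | m = 4 (0.0125) |
|---|---|---|---|---|
| 0.8 | 69.2% | 57.9% | 51.4% | 46.9% |
| 1.0 | 86.8% | 79.1% | 73.9% | 70.1% |

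The difference detectable with 80% power is 0.91 SD at 0.05, against 1.01, 1.07 and 1.10 SD for m = 2, 3 and 4.

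**Step 3: what Holm recovers.** Power for the slope by simulation of the 2×2 design:
- *All parameters differ by 0.8 SD* (m = 2 to 4, correlation 0.3 and 0.7): Bonferroni 47–58%, Holm 56–64%. The gain is about 6 points at m = 2 and 9 at m = 4.
- *Only the slope differs by 0.8 SD* (correlation 0 to 0.7): m = 2, Bonferroni 57.6–58.1% against Holm 57.9–58.4%; m = 4, 46.7–46.8% against 46.8–46.9%. The gain is at most 0.3 points.

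**Step 4: what a slope-first order recovers.** Here the slope is tested at 0.05 and the rest only if it is significant. The gain for the slope over Bonferroni, in percentage points, is:

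| d | m = 2 | m = 3 | m = 4 |
|---|---|---|---|
| 0.3 | 5.9 | 8.2 | 9.6 |
| 0.5 | 10.0 | 14.6 | 17.5 |
| 0.7 | 11.9 | 18.3 | 22.5 |
| 0.8 | 11.3 | 17.8 | 22.3 |
| 1.0 | 7.7 | 12.9 | 16.7 |
| 1.2 | 3.6 | 6.4 | 8.7 |

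The largest value on a finer grid is 22.7 points (m = 4, d = 0.74). The price falls on the others: if only one other parameter differs by 0.8 SD, its power drops from 47–58% to about 3%.

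**Step 5: family-wise error with no true differences.** Bonferroni and Holm coincide here, because Holm's first step is the Bonferroni test: 3.8–4.9% in simulation, lower with stronger correlation. Slope-first gives 5.0–5.1% in a simulation of 200,000 sets. All meet the nominal 5% within simulation error.

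**The case against.** **Bonferroni is valid.** It is conservative, simple, and gives simultaneous confidence intervals that Holm does not supply so readily. No false claim follows from using it. This stands, and it sets the weight of the point. The loss of simple intervals is minor.

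**The analysis is already done, so any change is post hoc.** This stands fully against moving the slope to 0.05 now. A fixed order controls the family-wise error only if it was set before the data were seen. Calling the slope primary does not document such an order. The objection does not reach Holm: Holm's rejections contain Bonferroni's, so even a late switch between the two stays within Holm's 5% bound.

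**Holm is not free in realised error.** When some parameters truly differ, Holm uses allowance that Bonferroni leaves unspent. With m = 2, uncorrelated tests and only the slope differing, the false-positive rate is about 4.0% against 2.5%. This is true, but both are inside the bound the plan set out to hold.

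**A stronger reading that the document does not support.** A reader might infer that the primary test loses 11 to 22 points of power which any sequential rule would restore. That range belongs only to a slope-first order, at an assumed 0.8 SD with 2 to 4 parameters. Holm gives far less, and close to nothing if the slope alone differs. Slope-first is also a trade-off against the other parameters rather than a pure gain.

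**Conclusion.** The point holds as one of efficiency. On the natural reading, the plan tests its primary parameter under single-step Bonferroni, and Holm on the same family is never worse at the same 5% bound.

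The direction is certain for any family of two or more. The size is not, since the number of parameters, alpha and the effect size are all unstated. Under the assumptions above, Holm adds between almost nothing and about 6 to 9 points. A slope-first order, if documented in advance, would add about 4 to 23 points over differences of 0.3 to 1.2 SD. All these figures are for the Group main effect; they change if the interaction is the effect of interest.

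The document does not support the inference that the Bonferroni rule is an error, or that the slope may now simply be judged at 0.05.

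**What to change.** Replace the multiplicity sentence with wording such as:

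> *The stimulus-response parameters tested were [list, with number]. For the [Group / Group by Condition] effect, p-values across these parameters were adjusted by Holm's method to hold the family-wise error at two-sided [alpha]. Unadjusted and Bonferroni-adjusted p-values are also reported.*

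The list must say whether the slope belongs to the family, and the sentence must name the ANOVA effect or effects covered.

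Only if dated documentation shows that the slope was to be tested first before the data were seen, use instead: slope at the full alpha, then Holm among the remaining parameters if the slope is significant, and those parameters descriptive otherwise.

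The Holm version costs one sentence and a re-reading of existing p-values, and gives up simple simultaneous intervals. The slope-first version also gives up any claim on another parameter when the slope is not significant.
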